7.8.1.2 AE summaries

An overall summary of adverse events will be presented.

The frequency of patients with adverse events will be summarised by treatment, primary SOC and PT.

AEs will also be reported by intensity. Separate tables will be provided:

- for patients with adverse events of special interest (AESI),
- for patients with serious adverse events,
- for patients with AEs leading to discontinuation,
- for patients with AEs leading to death,
- for patients with drug-related AEs.

The SOCs will be sorted according to the standard sort order specified by EMA, and PTs will be sorted by frequency (within SOC).

7.8.1.3 Analysis of hypoglycaemic events

The investigator will record for each AE whether it represents a hypoglycaemic event and, if so, record additional information to assess the intensity of the hypoglycaemic event. On the basis of this information the hypoglycaemic event will be classified as:

- confirmed hypoglycaemic adverse event are defined as hypoglycaemic adverse events that had a glucose concentration ≤ 70 mg/dL or required assistance.
- severe hypoglycaemia: event requiring assistance.
- hypoglycaemia event with blood glucose level <54 mg/dL (<3.0 mmol/L), even if asymptomatic.
- symptomatic hypoglycaemia, independent of the blood glucose value (this includes cases when the blood glucose was not measured during the event, but hypoglycaemia was diagnosed based on the clinical presentation).

The number of patients with hypoglycaemia according to investigator's judgement will be tabulated by treatment group. A subgroup analysis of confirmed events with respect to age category, rescue therapy and renal function will be performed.

The impact of treatment on the occurrence of hypoglycaemia will be explored using logistic regression model involving treatment and continuous baseline HbA1c. Time to the onset of the first hypoglycaemia will be estimated by Kaplan-Meier method. The logistic regression and Kaplan-Meier analysis will be performed on confirmed events as for all hypoglycaemia tables.

Summaries of hypoglycaemic events will include total number of hypoglycaemic events, descriptive hypoglycaemic event rate, number of episodes per patient, severity and intensity of the worst episode, action taken, minimum glucose level of worst episode, and time to onset of first episode. Hypoglycaemic events will also be summarised by baseline eGFR using MDRD formula, background medication and age group.

Different tables will be shown for (i) patients with investigator defined asymptomatic or symptomatic hypoglycaemia reported as AE, (ii) patients with confirmed hypoglycaemic adverse events, i.e. hypoglycaemic adverse events that had a plasma glucose concentration ≤ 70 mg/dL or required assistance, and, (iii) patients with minor, confirmed hypoglycaemic adverse events, defined as a hypoglycaemic event that had a plasma glucose concentration ≤ 70 mg/dL but did not require assistance.

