Drug-induced liver injury (DILI)	No risk of DILI was identified for empagliflozin. However, DILI generally can be severe and lead to fatal outcome or need of liver transplant. Therefore, careful monitoring and assessment of patients for potential DILI are needed.	Parameters for potential liver injury are included in the safety laboratory. Cases of liver impairment are defined as an AESI. Severe cases of liver impairment are adjudicated. (See Sections 5.2.3 , 5.2.6.1.4 and 8.7 ; details are also described in the adjudication charter).
Renal safety	In clinical trials in patients with DM, the incidence of renal impairment was similar to placebo. An initial decrease of estimated glomerular	Parameters for potential renal impairment are included in the safety laboratory.

Table 1.4.2:1 Known and potential risks of clinical relevance for the study population (cont.)

Possible or known risks of clinical relevance for this trial	Summary of data, rationale for the risk	Mitigation strategy
	
filtration rate (eGFR) was seen in patients treated with empagliflozin, which improved during continuous treatment or discontinuation of empagliflozin.
 
Cases of renal impairment, including those requiring dialysis, were reported in patients using SGLT2-inhibitors. Due to the renal mode of action and risk of volume depletion, the renal safety should be monitored.
	Cases of renal impairment are defined as an AESI (see Sections 5.2.3 and 5.2.6.1.4).
Trial procedures		
The patients who take placebo have a higher probability of treatment failure, i.e., of increase in HbA1c.	50% of patients will receive placebo.	This study will have criteria for rescue therapy (refer to Section 4.2.2) and patient discontinuation from study medication to ensure an adequate treatment in case of any clinical concern (refer to Section 3.3.4).
Hyperglycaemia	50% of patients will receive placebo and these patients thus have a higher probability of treatment failure, i.e., of increase in FPG and HbA1c.	Blood glucose will be monitored with SMBG. Appropriate inclusion/exclusion criteria of HbA1c and FPG values, as well as criteria for rescue therapy and patient discontinuation will ensure an adequate treatment in case of any clinical concern.

Table 1.4.2:1 Known and potential risks of clinical relevance for the study population (cont.)

Possible or known risks of clinical relevance for this trial	Summary of data, rationale for the risk	Mitigation strategy

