4.2 OTHER TREATMENTS, EMERGENCY PROCEDURES, RESTRICTIONS

4.2.1 Other treatments and emergency procedures

Throughout the duration of the trial, patients should continue to take their previous antidiabetic therapy as permitted by trial protocol, including acceptable OADs with the exception of SGLT-2 inhibitors (treatment with insulin and GLP-1 agonists is excluded as well, see Section [4.2.2](#)). This background medication of OADs should remain unchanged throughout the study. The background medication will not be provided as part of the clinical trial supplies.

The patients can take their background medication as they are used to and should have the same habits of dosing throughout the trial. Morning dose of OADs and study medication should be taken after the visits blood samples are taken.

Hyperglycaemia

Rescue medication can be given if the criterion below is met during the run-in period at the investigator's discretion. Patients who need rescue medication prior to Visit 3 are not eligible for randomisation. Please see Section [3.3.4.1](#):

- The patient has a glucose level >200 mg/dL (>11.1 mmol/L) after an overnight fast

Rescue medication, for the treatment of hyperglycaemia, can be initiated during the double-blind treatment period of the trial (i.e., from Visit 3 to Visit 8) at the investigator's discretion if the criterion below is met:

- The patient has a glucose level >200 mg/dL (>11.1 mmol/L) after an overnight fast

The above results should be confirmed, meaning that there is a minimum of two measurements, at least second measurement should be performed at the investigational site after an overnight fast (central or local laboratory testing is allowed), and on a different day to the initial measurement.

In order to expedite the rescue medication initiation decision, the investigator may confirm the results (second measurement) at the local or commonly used laboratory. This procedure with its results should be documented in the patient's medical chart. Before initiation of rescue therapy a FPG sample should be drawn and sent to the central lab for analysis.

If the above criteria are met, the initiation of rescue medication is at the Investigator's discretion, based on the patients' current clinical condition (e.g., ongoing illness etc.). If dose of standard of care increase, it should be recognised as rescue medication.

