Rescue medication can be used from when it is initiated until the end of the trial. The choice of rescue medication and its dosage will be left to the discretion of the investigator excluding SGLT-2 inhibitors. Regardless of the choice made, rescue medication should be taken in accordance with the prescribing information of that respective medication, taking into account potential contraindications.

In the case of hypoglycaemic event that may put patient on risk (e.g., repeated symptomatic hypoglycaemic events or severe hypoglycaemic event), appropriate adjustment of oral antidiabetic therapy such as a dose reduction/discontinuation of ongoing rescue medication should be initiated.

If, in the investigator's clinical opinion, no further effect from the rescue medication is anticipated, and the patient's hyper- or hypoglycaemia cannot be controlled, the patient should be discontinued from the trial as specified in Section [3.3.4](#).

Any rescue medications should be recorded in the source documents and on the appropriate pages of the eCRF.

Rescue medication will not be provided as part of the clinical trial supplies.

Special attention must be paid to the prevention of DKA. All patients must be made aware of this risk and need to be instructed to contact the investigator or other healthcare professional in case of symptoms of DKA.

In case of a suspected DKA the investigator should ensure that appropriate tests are performed at the earliest opportunity according to guidelines in Japan, such as a blood gas test (i.e., pH, bicarbonate, anion gap, potassium, blood glucose, etc; the results will be collected on the relevant page of the eCRF) and that the patient is appropriately treated (i.e., hospitalised or referred to emergency treatment) according to treatment guidelines in Japan.

Any additional treatment, that does not qualify as a rescue medication, and is considered necessary for the patient's welfare may be given at the discretion of the investigator. Exceptions to this are the restrictions described in Section [4.2.2](#).

There are no special emergency procedures to be followed.

4.2.2 **Restrictions**

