7. PLANNED ANALYSIS

Disposition of the patient population participating in the trial will be analysed by treatment groups and presented in the clinical trial report as a frequency-distribution.

A frequency of patients with iPDs, also summarised by whether the iPD led to exclusion from the PPS, will be presented by treatment group for the RS. The frequency of patients in different analysis sets will also be analysed for each treatment group.

For in-text tables presenting descriptive analysis of the endpoints and other variables (analysed in original scale), the set of summary statistics is: N (number of patients with nonmissing values), mean, SD.

For end-of-text tables, the set of summary statistics is: N (number of patients with nonmissing values) / Mean / SD / Min / Q1) / Median / Q3 / Max.

Statistical parameters will be displayed to a defined number of decimal places as specified in the BI guideline “Standards for Reporting of Clinical Trials and Project Summaries” (6).

Tabulations of frequencies for categorical data will include all possible categories and will display the number of observations in a category as well as the percentage (%) relative to the respective treatment group. Percentages will be rounded to one decimal place. The category missing will be displayed if and only if there are actually missing values. Percentages will be based on all patients in the respective patient set whether they have non-missing values or not.

In all specified statistical analyses, treatment comparisons will be made between randomised empagliflozin group and placebo.

Descriptive statistics on the impact of COVID-19 on study visits as well as trial medication intake will be provided if any.

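### Confirmed hypoglycaemia is to be split by rescue therapy, a post-randomisation factor that treatment affects, and the all-patient hypoglycaemia analyses keep post-rescue events with no cut-off at rescue

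*SAP*

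**What the plan says.** On confirmed hypoglycaemia, SAP 7.8.1.3 says: "A subgroup analysis of confirmed events with respect to age category, rescue therapy and renal function will be performed". SAP 7 adds that in all specified statistical analyses "treatment comparisons will be made between randomised empagliflozin group and placebo", so the natural reading is empagliflozin against placebo within each rescue stratum.

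Four protocol statements fix what rescue is:

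- **Timing (4.2.1):** "Patients who need rescue medication prior to Visit 3 are not eligible for randomisation".
- **Trigger (4.2.1):** "The patient has a glucose level >200 mg/dL (>11.1 mmol/L) after an overnight fast". It must be confirmed on a different day, and starting rescue is then at the investigator's discretion.
- **Link to treatment (1.4.2):** "50% of patients will receive placebo and these patients thus have a higher probability of treatment failure, i.e., of increase in FPG and HbA1c".
- **Drug (4.2.1):** "The choice of rescue medication and its dosage will be left to the discretion of the investigator excluding SGLT-2 inhibitors". A dose increase of standard of care also counts as rescue, and rescue may run to the end of the trial.

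For the all-patient analyses, SAP 7.8.1.1 assigns adverse events to treatment from first intake until 7 days after last intake, with no cut at rescue. The logistic model in SAP 7.8.1.3 contains treatment and baseline HbA1c only. No censoring at rescue is stated for the Kaplan-Meier analysis. SAP 6.6.1 applies its rescue censoring rule to the OC and LOCF analyses only.

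**The concern.** There are two separate problems.

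**The split.** Unlike age or baseline renal function, rescue status is a consequence of randomised treatment. Patients rescued despite empagliflozin are a more extreme group than patients rescued on placebo. Patients who stay unrescued on placebo are the better-controlled part of their arm. If underlying glycaemia also affects hypoglycaemia risk, the arms differ in risk within both strata even when the drug does nothing to hypoglycaemia.

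**The all-patient tables and models.** These respect randomisation, but they count events on rescue drugs against the randomised arm. If rescue is commoner on placebo and rescue drugs cause hypoglycaemia, placebo gains events and empagliflozin looks safer by comparison. The protocol foresees such events: after risky hypoglycaemia, "dose reduction/discontinuation of ongoing rescue medication should be initiated". Protocol 1.4.2 also names hypoglycaemia as a risk, higher with sulfonylureas or glinides.

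At stake is how a named risk is read in patients aged 65 or older.

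**Working it through.** **The plan's own figure.** The documents give no rate for rescue or hypoglycaemia. The only relevant stated figure is the sample size in Protocol 7.5. With a difference of 0.5, SD 0.85 and two-sided 5%, a two-sample t-test has 89.7% power at 61 per arm and 90.1% at 62. Then 62 / 0.97 = 63.9, which rounds up to 64. The figure reproduces and this point does not touch it.

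**Step 1: bias in the split (all inputs assumed).** Let U ~ N(0,1) be underlying glycaemia.

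- Hypoglycaemia: logit(p) = -2.5 - 0.8U in both arms, so the drug has no effect on it. The odds rise by exp(0.8) = 2.2 per SD of better control. Overall risk is 9.5% in each arm and the overall OR is 1.
- Rescue: on-trial glycaemia exceeds a threshold t. It is U on placebo and U - 0.6 on empagliflozin, without or with within-patient noise of SD 0.5.
- Without noise, P(rescue) = 1 - Φ(t) on placebo and 1 - Φ(t + 0.6) on empagliflozin. With noise, the argument is divided by √1.25 = 1.118.

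Integrating over U gives:

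| t | noise SD | rescue, placebo / empagliflozin | OR unrescued | OR rescued |
|---|---|---|---|---|
| 1.0 | 0 | 15.9% / 5.5% | 0.91 | 0.66 |
| 1.4 | 0 | 8.1% / 2.3% | 0.95 | 0.65 |
| 1.0 | 0.5 | 18.6% / 7.6% | 0.91 | 0.72 |
| 1.4 | 0.5 | 10.5% / 3.7% | 0.94 | 0.72 |

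For the third row, the rescued risks are 2.30% (empagliflozin) and 3.15% (placebo): OR = (0.0230/0.9770)/(0.0315/0.9685) = 0.72. The unrescued risks are 10.09% and 10.94%: OR = (0.1009/0.8991)/(0.1094/0.8906) = 0.91.

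A second model checks sensitivity. It assumes 5% baseline risk, a correlation of 0.7 between U and the rescue trigger, and a hypoglycaemia slope b of 0.5 to 1 per SD.

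| rescue, empagliflozin / placebo | OR unrescued | OR rescued |
|---|---|---|
| 2% / 6% | 0.97-0.98 | 0.73-0.86 |
| 3% / 15% | 0.91-0.94 | 0.60-0.78 |
| 5% / 30% | 0.82-0.89 | 0.52-0.73 |

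In this model the bias is zero if rescue is equally likely in both arms (10% / 10%) or if b = 0.

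**Step 2: can it be seen at 64 per arm?** In the third row of the first table, the rescued stratum expects 64 × 0.1855 × 0.0315 = 0.37 placebo and 64 × 0.0762 × 0.0230 = 0.11 empagliflozin patients with an event, 0.49 together before rounding. The chance of none in either arm is (1 - 0.00584)^64 × (1 - 0.00175)^64 = 0.61. The unrescued stratum expects 5.70 and 5.97 such patients among 52.1 and 59.1. The SE of log OR is √(1/5.70 + 1/46.4 + 1/5.97 + 1/53.1) = 0.62, so the 95% interval runs about exp(1.96 × 0.62) = 3.4-fold either way.

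**Step 3: rescue-drug events in the all-patient analysis.** Take the second model with b = 0, a drug with no effect, rescue 3% / 15%, and a rescue drug that triples the odds. Risk off rescue is 5%. On rescue the odds are 3 × 0.0526 = 0.158, a risk of 13.6%.

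- Empagliflozin: 0.97 × 0.05 + 0.03 × 0.136 = 0.0526
- Placebo: 0.85 × 0.05 + 0.15 × 0.136 = 0.0630
- OR = (0.0526/0.9474)/(0.0630/0.9370) = 0.83

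With rescue odds ratios of 3 to 6 and b from 0 to 1, the overall OR is 0.87-0.98 at 2% / 6%, 0.69-0.93 at 3% / 15% and 0.53-0.83 at 5% / 30%. If the drug truly doubles the odds (b = 0.5 to 1), the overall OR is 1.90-1.98 when rescue drugs cause no hypoglycaemia. It falls to 1.51-1.77 (3% / 15%) or 1.16-1.58 (5% / 30%) when they do.

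**Step 4: does ending time at risk at rescue remove the selection?** Not fully. In the third row of the first table, let event and rescue times be uniform over follow-up (a further assumption), so half of rescued patients' events and time precede rescue.

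- Placebo: (0.8145 × 0.1094 + 0.5 × 0.1855 × 0.0315)/(1 - 0.5 × 0.1855) = 0.1014
- Empagliflozin: (0.9238 × 0.1009 + 0.5 × 0.0762 × 0.0230)/(1 - 0.5 × 0.0762) = 0.0978

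The rate ratio is 0.96. Across the four rows it is 0.96-0.98, where the truth is 1.

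**The case against.** The case for leaving the plan alone has real substance.

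- **Safety analyses are descriptive.** Protocol 7.2.5 plans no hypothesis testing, and SAP 7.8.1.3 specifies no model or odds ratio for this subgroup. This stands and limits the consequence. It does not make the strata comparable.
- **Rescue may be rare.** Fasting glucose above 200 mg/dL in run-in is an exclusion, rescue needs confirmation, and Protocol 3.2 calls the risk of significant hyperglycaemia low. This also stands: at 2% / 6% rescue the unrescued OR is 0.97-0.98.
- **The definition is not visible.** SAP 5.3.2 and 6.4 are not in the public text, and a subgroup analysis of events could mean events before against after rescue. Under any definition, however, rescue follows randomisation. If the event-level reading is meant, the SAP should say so and define the time at risk.
- **Deleting the split loses information.** This is fair, and a labelled description without an arm contrast would keep it.

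A reader might infer that the split itself blurs the drug's risk with rescue-drug events. It does not: the unrescued stratum contains no such events, and the blurring arises in the all-patient tables and models. A reader might also infer that rescue drugs are unrestricted. Protocol 4.2.1 excludes SGLT-2 inhibitors, and 4.2.2.1 prohibits insulin, GLP-1 agonists and other diabetes drugs beyond standard of care during the trial. Those two sections do not agree.

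**Conclusion.** The point holds, with modest consequences. Rescue therapy is not a valid between-arm subgroup factor for hypoglycaemia, and the readable SAP has no analysis that clearly separates events before rescue from events after it.

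The size cannot be taken from the documents. Under the first model's assumptions (rescue 8-19% on placebo and 2-8% on empagliflozin, a drug with no effect), the OR is about 0.91-0.95 unrescued and 0.65-0.72 rescued. Both lean towards making empagliflozin look safer. That direction rests on better underlying control raising hypoglycaemia risk. The masking in the all-patient analyses additionally needs rescue drugs that cause hypoglycaemia.

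It would be tempting to conclude that the trial's hypoglycaemia table will show a visibly false result. At 64 per arm it probably would not: the rescued stratum expects under one event, and random error in the unrescued stratum dwarfs the bias. Nor is there any effect on the primary endpoint, alpha or power. The all-events randomised comparison remains valid for the whole strategy of study drug plus rescue as used. What is weak is reading the drug's own risk from it, or from the split.

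**What to change.** In SAP 7.8.1.3:

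1. Remove rescue therapy from the subgroup list and keep age category and renal function, both taken at baseline. At minimum, show rescue only as a non-randomised description without an arm contrast.
2. Keep the all-events comparison by randomised arm as the main analysis.
3. Add, as supportive, confirmed hypoglycaemia with time at risk ending at the start of rescue: incidence, exposure-adjusted rate and Kaplan-Meier. List events after rescue separately by arm.
4. State which definition and start date of rescue applies here, since the rule in SAP 6.6.1 is written for the OC and LOCF analyses.
5. State that censoring at rescue may itself be informative (rate ratio 0.96-0.98 instead of 1 in the illustration), so this analysis does not replace the main one.

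Separately, Protocol 4.2.1 (permitted rescue drugs) and 4.2.2.1 (prohibited drugs) must be reconciled, because together they determine which rescue drugs can contribute events.

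The cost is SAP wording and limited programming for the added table, curve and listing. Protocol 4.2.1 already requires rescue medication to be recorded in the eCRF, so no new data are needed.

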1.4.2 Risks

Table 1.4.2: 1 displays the anticipated side effects of the study drugs, based on the mechanism of action, on the observed clinical data from ongoing studies, and on published clinical data.

Table 1.4.2:1 Known and potential risks of clinical relevance for the study population

Possible or known risks of clinical relevance for this trial	Summary of data, rationale for the risk	Mitigation strategy
Investigational Medicinal Product: empagliflozin		
Hypoglycaemia	The risk of hypoglycaemia is considered to be low. However, when empagliflozin is used concomitantly with sulfonylurea and/or glinides, possibly increasing the risk of hypoglycaemia.	Patients in treatment with insulin are excluded from the study. Guidance for the investigator provided in the IB [c01678844]. Blood glucose will be monitored with SMBG.
Volume depletion	Empagliflozin may selectively reduce interstitial volume with minimal change in intravascular volume Polyuria and consequent dehydration and hypotension were identified as risks in	Guidance for the investigator provided in the IB [c01678844]. Information and recommendations for the patients provided in the informed consent form (ICF).

Table 1.4.2:1 Known and potential risks of clinical relevance for the study population (cont.)

Possible or known risks of clinical relevance for this trial	Summary of data, rationale for the risk	Mitigation strategy
	patients treated with empagliflozin, especially in patients with known cardiovascular disease, history of hypotension, taking diuretics or other antihypertensive drugs, or elderly patients aged 75 years and older [P19-02151] .	

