3.3.2 Inclusion criteria

1. Japanese¹ patients with diagnosis of T2DM prior to informed consent

¹ Japanese is defined as patient has parents who are Japanese.

Proprietary confidential information © 2020 Boehringer Ingelheim International GmbH or one or more of its affiliated companies

2. HbA1c $\geq 7.0\%$ and $\leq 10.0\%$ for patients at Visit 1 (screening)
If the patient is on treatment with oral antidiabetic drug(s) potentially associated with severe hypoglycaemia (e.g., sulfonylurea or glinides), the following HbA1c value is used as criterion
 - 1) HbA1c $\geq 7.5\%$ and $\leq 10.0\%$ for age ≥ 65 and < 75
 - 2) HbA1c $\geq 8.0\%$ and $\leq 10.0\%$ for age ≥ 75
3. Patients on diet and exercise regimen who are drug-naïve² or on treatment with any oral antidiabetic drug (OAD) other than Glucagon-Like Peptide-1 (GLP-1) agonists and SGLT-2 inhibitor. Antidiabetic therapy has to be unchanged for 12 weeks prior to randomisation (any thiazolidinedione therapy has to be unchanged for at least 18 weeks prior to informed consent).
4. Age ≥ 65 years at informed consent
5. BMI $\geq 22 \text{ kg/m}^2$ at Visit 1 (screening)
6. Male or post-menopausal³ female patients
7. Patient signed and dated written informed consent in accordance with ICH-GCP and local legislation prior to admission to the trial

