7.4 RANDOMISATION

The trial will be performed as a double-blind design with respect to the two blinded treatment groups. Randomisation to the two treatment groups of empagliflozin 10 mg and placebo will be 1:1 and will be stratified by following 2 factors:

- HbA1c (<8.5 or \geq 8.5%) at Visit 1
- Age (\geq 65 to <75 or \geq 75 years) at Visit 1

The randomisation of patients to the treatment groups will be performed via an IRT system.

BI will arrange for the randomisation and the packaging and labelling of trial medication. The randomisation list will be generated using a validated system, which involves a pseudo-random number generator and a supplied seed number so that the resulting allocation of

treatment will be both reproducible and non-predictable. The block size will be documented in the clinical trial report. Access to the randomisation codes will be controlled and documented.

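### The exploratory hypoglycaemia model omits baseline sulfonylurea/glinide use, so a chance imbalance in background drug can shift the treatment odds ratio; the shift is small beside the sampling error, and one SAP sentence removes it

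*SAP*

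**What the plan says.** SAP 7.8.1.3 states that the impact of treatment on hypoglycaemia will be "explored using logistic regression model involving treatment and continuous baseline HbA1c". It fixes the outcome as confirmed events: "The logistic regression and Kaplan-Meier analysis will be performed on confirmed events as for all hypoglycaemia tables". No other covariate is named.

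Background drug enters that section only descriptively: "Hypoglycaemic events will also be summarised by baseline eGFR using MDRD formula, background medication and age group". The subgroup analysis of confirmed events listed there covers age category, rescue therapy and renal function, and does not include background drug.

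The protocol treats background drug as important for this outcome in two places.
- Table 1.4.2:1 (Section 1.4.2) calls the hypoglycaemia risk low in general, but adds a caveat: "when empagliflozin is used concomitantly with sulfonylurea and/or glinides, possibly increasing the risk of hypoglycaemia".
- Inclusion criterion 2 (Section 3.3.2) sets a separate entry rule for patients on "oral antidiabetic drug(s) potentially associated with severe hypoglycaemia (e.g., sulfonylurea or glinides), the following HbA1c value is used as criterion". Their minimum HbA1c is 7.5% below age 75 and 8.0% from age 75, against 7.0% for other patients.

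Protocol 7.4 says randomisation "will be stratified by following 2 factors", and these are HbA1c (below 8.5%, or 8.5% and above) and age (below 75, or 75 and above). Protocol 7.2.5 plans safety analyses as descriptive, without hypothesis tests.

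**The concern.** If the sponsor fits a model for the treatment effect on hypoglycaemia, its covariates should be the strong baseline predictors of that outcome. The protocol identifies one and changes eligibility because of it, yet neither the randomisation nor the model handles it.

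Baseline HbA1c is a poor substitute. Under the entry rule, sulfonylurea/glinide users start at higher HbA1c. Higher glucose should lower the risk of hypoglycaemia while the background drug raises it, so the single HbA1c slope mixes two opposing effects and adjusts well for neither.

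At stake is how the odds ratio for confirmed hypoglycaemia in elderly patients is read. If one arm happens to hold more users, part of the apparent drug effect is background drug. The primary endpoint is untouched.

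**Working it through.** **Inputs from the documents.** 64 patients randomised per arm (Protocol 7.5). That section plans 62 evaluable per arm for a difference of 0.5 and SD of 0.85 at two-sided 5%. A two-sample t-test with 62 per arm has power 90.1%, and 62/0.97 = 63.9, so 64 reproduces. This figure concerns HbA1c only; no design figure is given for hypoglycaemia.

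**Assumptions.** The documents give neither the share of sulfonylurea/glinide users nor any event risk. I take a share of 20 to 40%, risk of 5 to 15% in users and 1 to 3% in non-users, no drug effect, and all 64 per arm treated.

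**Step 1: chance imbalance.** The SD of the between-arm difference in share is sqrt(2p(1-p)/64). This ignores the stratification; any association between drug use and the strata would narrow it somewhat.

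| Share p | SD | P(difference of 10 points or more, either direction) |
|---|---|---|
| 20% | 0.071 | 0.16 |
| 30% | 0.081 | 0.22 |
| 40% | 0.087 | 0.25 |

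Half of these go in each direction, so an excess of 10 points or more in the empagliflozin arm has probability of about 8 to 12%.

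**Step 2: crude odds ratio from the imbalance alone.** Take 35% against 25% use. Risk in an arm = share × user risk + (1 - share) × non-user risk.
- User risk 15%, non-user 1%: 0.35×0.15 + 0.65×0.01 = 0.059; 0.25×0.15 + 0.75×0.01 = 0.045; odds ratio 1.33.
- User risk 5%, non-user 3%: 0.35×0.05 + 0.65×0.03 = 0.037; 0.25×0.05 + 0.75×0.03 = 0.035; odds ratio 1.06.

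The other combinations fall between these two.

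**Step 3: sampling error at the upper end.** Risks of 5.9% and 4.5% in 64 patients are 3.8 and 2.9 patients, a difference of 0.9. SE of the log odds ratio = sqrt(1/3.78 + 1/60.22 + 1/2.88 + 1/61.12) = 0.80. The log odds ratio is 0.286, or 0.36 SE. 95% CI: exp(0.286 ± 1.96×0.80), about 0.28 to 6.4.

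**Step 4: the planned model against the extended one.** Trials of 128 patients were simulated with shares of 20% and 40%, a true HbA1c slope of -0.30 on the log-odds scale, no drug effect, and Firth fits for both models.
- For user risks of 5 to 15%, each 10-point excess of users in the empagliflozin arm moved the treatment log odds ratio by +0.10 to +0.27 in the planned model (odds ratio ×1.10 to ×1.31).
- With sulfonylurea/glinide use added, the movement was -0.05 to +0.02 (×0.95 to ×1.02).
- Including a user risk of 30% as an extreme, the planned model returned an HbA1c slope of -0.04 to +0.16; the extended model returned -0.29 to -0.40.
- Over all randomisations both models were centred near zero (mean log odds ratio -0.06 to +0.02).
- The imbalance explained 1 to 14% of the variance of the planned model's estimate, whose SD was about 0.5 to 1.1, because only about 3 to 17 patients per trial had events.
- False-positive rates were about 3% or less in both models.

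**The case against.** The strongest reply is that little rests on this model. It is labelled exploratory, Protocol 7.2.5 rules out hypothesis tests for safety, and the summary by background medication lets a reader see an imbalance and the event rates within each group. All of that stands, and it keeps the point minor. A descriptive summary still gives no adjusted treatment comparison, which is what the model is there to provide.

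A reader might infer that the planned estimate is biased, or that the hypoglycaemia result could be driven by which arm drew more users. Neither is supported. Randomisation keeps the estimate centred, and any imbalance is a modest part of a very imprecise estimate. The accurate word is shifted.

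The caveat in Table 1.4.2:1 concerns empagliflozin taken together with these drugs. A main-effect covariate assumes a common odds ratio and cannot show a combination effect. That is correct, and it is why the adjusted model should be read beside the summary by background medication.

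It could also be said that events are too few for another covariate. With ordinary maximum likelihood that is a fair worry; a penalised fit answers it. The same sparsity counts against going further. Kaplan-Meier curves by treatment within user and non-user groups may look attractive, but at 30% use with risks of 15% and 1% there would be about 128×0.3×0.15 = 5.8 events in users and 128×0.7×0.01 = 0.9 in non-users, too few to plot usefully.

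Finally, SAP Section 6.4 is not in the public text and may define background-medication categories. The model as written does not use them.

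**Conclusion.** The point holds as a cheap improvement. The model leaves out the baseline factor that the protocol itself links to hypoglycaemia, and HbA1c does not stand in for it. The consequence depends on the imbalance that occurs: under the assumed ranges, a 10-point excess of users corresponds to a crude odds ratio of 1.06 to 1.33 with no drug effect, or a factor of 1.10 to 1.31 in the simulated planned model. Both are small against a confidence interval that spans more than a twentyfold range. The sizes rest on assumed usage shares and event risks. The omission itself rests only on the text of SAP 7.8.1.3 and Protocol 7.4. The primary analysis and the trial's conclusions on HbA1c are unaffected.

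**What to change.** In SAP 7.8.1.3, change the logistic model to treatment + continuous baseline HbA1c + baseline sulfonylurea/glinide use (yes/no), fitted with Firth's penalised likelihood because events are few. State that it will be read alongside the planned summary of events by background medication. Make the change before unblinding, so that the covariate is not chosen after the result is known.

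The cost is SAP wording only. Baseline therapies are already summarised (SAP 7.2), and background medication is already used to tabulate hypoglycaemia. The downside is one more parameter in a sparse model and a slightly less precise treatment estimate: in the simulations with no drug effect, the SD of the log odds ratio rose from 0.53–1.08 to 0.57–1.12.
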